3.7 Identification of Source Data

The following source data will be directly recorded in the Electronic Medical Record (EMR)

- Vital signs
- Serious Adverse Events
- Demographic Data
- Baseline Transplant and Followup
- Information related to the Janssen Ad26.CoV2.S vaccine administration and side effects
- Medications
- Patient Status
- Patient Graft Status
- Laboratory and biopsy results and clinical interpretation of the values
- Nephrology and Transplant related clinical visits
- Clinical visits related to Transplant

The following data will be obtained from the subject and maintained in the study files

- Study Diary
- Risk Factor Assessment and Kidney Transplant Follow Up Questionnaire
- Pre and Post Vaccination Symptoms Questionnaire
- Safety Follow Up Questions
- COVID-19 Surveillance and Evaluation
- Follow Up Safety Assessment Phone Calls

Mechanistic study results will be obtained from 3 sources:

- 1) Reported within SOFTLab which is the Mayo data repository for research data from clinical labs. This involves the reporting of results for the following assays:
 - a. Total Immunoglobulin levels
 - b. T-cell and B-cell Immunophenotyping.
 - c. COVID T-cell ELISPOT
 - d. T-cell repertoire.
- 2) Reported directly from [name] laboratory:
 - a. Covid Memory B-cell.
- 3) Reported directly from Imanis Life Sciences:
 - a. Neutralizing antibody.

Regardless of the source, all source documents will be stored by the Mayo study team.

4 Subject Selection Enrollment and Withdrawal

4.1 Inclusion Criteria

Criteria for Entry into the Study:

- Any kidney transplant recipient from Mayo Clinic who has received at least two doses of the mRNA vaccine (two or more doses of mRNA vaccine-Moderna or Pfizer) and are >28 days after most recent vaccination at the time of spike protein assessment.
- Recipients of a kidney transplant, including those transplanted with other solid organ transplants in addition to the kidney. Subjects may have received more than 1 kidney transplant.
- More than 90 days since any transplant including a kidney transplantation.
- ≥ 18 years of age on the day of consent.

Criteria for Entry into Segment I

- Must have a Roche Elecsys® Anti-SARS-CoV-2 S level of <250 U/mL to be eligible for Segment I.
- Platelet count of >75,000/ μ L on the day of vaccination with the Janssen Ad26.CoV2.S vaccine.
- Contraceptive (birth control) use should be consistent with local regulations regarding the acceptable methods of contraception for those participating in clinical studies.
- Before randomization, participants must be either:

- Not be of childbearing potential
- Of childbearing potential and practicing an acceptable effective method of contraception. Subject must agree to remain on contraception from date of consent until 3 months after the last dose of the Janssen Ad26.CoV2.S vaccine. Use of hormonal contraception should start at least 28 days before the 1st administration of the Janssen Ad26.CoV2.S vaccine. The sponsor-investigator should evaluate the potential for contraceptive method failure (for example, noncompliance, recently initiated) in relationship to the Janssen vaccination. Acceptable effective method a for this study include:
 - Hormonal contraception:
 - Combined (estrogen and progestogen containing) hormonal contraception associated with inhibition of ovulation (oral, intravaginal, or transdermal)
 - Progestogen-only hormonal contraception associated with inhibition of ovulation (oral, injectable, or implantable)
 - Intrauterine device
 - Intrauterine hormone-releasing system
 - Bilateral tubal occlusion/ligation procedure
 - vasectomized partner (the vasectomized partner should be the sole partner for that participant)
 - Sexual abstinence (defined as refraining from heterosexual intercourse from the date of consent until 3 months after the last dose of the Janssen Ad26.CoV2.S vaccine. The reliability of sexual abstinence needs to be evaluated in relation to the duration of the study and the preferred and usual lifestyle of the participant.).
- Note:** Use of condoms is **not** considered as an acceptable contraceptive barrier method due to the failure rate of female and male condoms (Centers for Disease Control and Prevention. Reproductive Health: Contraception. <https://www.cdc.gov/reproductivehealth/contraception/index.htm>. Accessed 23 November 2020)
- If subject is female and of childbearing potential, she must:
 - Have a negative highly sensitive serum pregnancy test prior to vaccination.
- Participant agrees to not donate bone marrow, blood, and blood products from the first Janssen Ad26.CoV2.S vaccine administration until 3 months after the last dose of the Janssen Ad26.CoV2.S vaccine.

4.2 Exclusion Criteria

- Clinically significant acute illness (this does not include minor illnesses such as diarrhea or mild upper respiratory tract infection) or temperature $\geq 38.0^{\circ}\text{C}$ (100.4°F) within 24 hours prior to the planned 1st dose of the Janssen Ad26.CoV2.S vaccine; randomization at a later date is permitted at the discretion of the sponsor-investigator.

- Has a known or suspected allergy or history of anaphylaxis or other serious adverse reactions to vaccines or their excipients (including specifically the excipients of the Janssen Ad26.CoV2.S vaccine; refer to the Investigative Brochure).
- Subject has received or plans to receive:
 - Licensed live attenuated vaccines –within 28 days before or after planned administration of the 1st or subsequent Janssen vaccinations.
 - Other licensed (not live) vaccines –within 14 days before or after planned administration of the 1st or subsequent Janssen vaccinations.
- Received an investigational drug within 30 days (including investigational drugs for prophylaxis of COVID-19) or used an invasive investigational medical device within 30 days of the Janssen Ad26.CoV2.S vaccine. Received investigational Immunoglobulin (Ig) or investigational monoclonal antibodies within 3 months, or received convalescent serum for COVID-19 treatment within 4 months or received an investigational vaccine (including investigational Adenoviral- vectored vaccines) within 6 months before the planned administration of the 1st dose of the Janssen Ad26.CoV2.S vaccine or is currently enrolled or plans to participate in another investigational study within 3 months after the last Janssen vaccination.

Note: Participation in an observational clinical study is allowed at the sponsor-investigator's discretion; please notify the sponsor-investigator of this decision.

Efforts will be made to ensure inclusion of participants who have not been previously enrolled in coronavirus studies. In order to participate subject must agree and understand that they cannot enroll in other coronavirus focused studies while participating in this one.

- Is pregnant or planning to become pregnant at the time of consent and within 3 months of the last dose of the Janssen Ad26.CoV2.S vaccine.
- Has a history of an underlying clinically significant acute or chronic medical condition or physical examination findings which, in the opinion of the sponsor-investigator, would make study participation not be in the participant's best interest (e.g., compromise the well-being) or that could prevent, limit, or confound the protocol-specified assessments.
- Has a contraindication to IM injections and blood draws.
- Has had major psychiatric illness, which in the sponsor-investigator's opinion would compromise the participant's safety or compliance with the study procedures.
- Cannot communicate reliably with the sponsor-investigator or comply with study procedures.
- In the opinion of the sponsor-investigator, is unlikely to adhere to the requirements of the study or is unlikely to complete the full course of protocol required vaccination and observation.
- History of cancer malignancy within 1 year before screening (exceptions are squamous and basal cell carcinomas of the skin and carcinoma in situ of the cervix, or other malignancies with minimal risk of recurrence).
- History of acute polyneuropathy (e.g., Guillain-Barré syndrome)
- Chronic history of platelet count <75,000/ μ L.
- History of thrombosis with thrombocytopenia syndrome (TTS) or heparin-induced thrombocytopenia (HIT).
- History of capillary leak syndrome (CLS).
- History of myocarditis or pericarditis.

- Received pre-exposure prophylactic medications for COVID-19 that could interfere with assessments of any study-related endpoint.

4.3 Subject Recruitment, Enrollment and Screening

Kidney transplant recipients who have received at least two of the mRNA vaccines will be identified by review of their medical record to see if they preliminary fit other inclusion/exclusion criterion for the study. If they appear to be a potential subject they will be contacted via phone or the Mayo Clinic portal to determine interest in study participation. If the potential participant is interested, they will be consented in person or remotely and instructed on study procedures.

Consented subjects will submit a blood sample to determine if they fit the enrollment criterion for the anti-SARS-CoV-2 spike protein level (<250U/ml). Those with an anti-SARS-CoV-2 spike protein levels at <250U/ml will receive the Janssen Ad26.CoV2.S vaccine.

This study plans to enroll up to 1200 research subjects to obtain 400 that have low or no detectable anti-SARS-CoV-2 spike protein antibody levels. Based on prior small studies, we expect (conservatively) that at least 20% will have low, but detectable antibody levels and 30% of all patients will have no detectable levels and will meet this inclusion criteria and other inclusion criteria. Thus, we envision screening approximately 1,200 kidney transplant recipients. Screening will be completed once 400 subjects have enrolled in Segment I.

4.4 Early Withdrawal of Subjects

4.4.1 When and How to Withdraw Subjects

Vaccination with the Janssen Ad26.CoV2.S vaccine will be withheld from participants from Segment I for the reasons listed below. These participants must not receive any further doses of the Janssen Ad26.CoV2.S vaccine but can remain in the study for follow-up assessments of safety and immunogenicity. Additional unscheduled visits may be performed for safety/reactogenicity reasons, if needed. In case of questions, the study staff at Mayo Arizona, Florida or Rochester are encouraged to contact the sponsor-investigator.

- Any related AE, worsening of health status or intercurrent illness that, in the opinion of the sponsor-investigator, requires discontinuation from the Janssen Ad26.CoV2.S vaccine
- The participant becomes pregnant
- Withdrawal of consent to receive the Janssen Ad26.CoV2.S vaccine
- Anaphylactic reaction following vaccination with the Janssen Ad26.CoV2.S vaccine, not attributable to causes other than vaccination
- SAE or other potentially life-threatening (Grade 4) event that is determined to be related to the Janssen Ad26.CoV2.S vaccine
- Participant previously experienced TTS or HIT
- Participant previously experienced myocarditis and/or pericarditis.

A participant will be withdrawn from the study for any of the following reasons:

- Lost to follow-up
- Withdrawal of Consent from the study
- Repeated failure to comply with protocol requirements
- Death

If a participant is withdrawn from the study, or chooses to no longer participate, no further study data will be acquired but their clinical care will continue as usual.

If a patient is withdrawn, but has already received the Janssen Ad26.CoV2.S vaccine, they will not be replaced by another patient.

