3.3 Duration of Participation

Subjects who only participate in Segment I will be followed for 2 years after receiving the Janssen Ad26.CoV2.S vaccine. Those who participate in Segment II will have their participation extended, with 2 years of clinical follow up after receiving the second Janssen Ad26.CoV2.S vaccine date. Screened patients not receiving the Janssen Ad26.CoV2.S vaccine will be followed for 2 years.

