5.5 Subject Compliance Monitoring

Study vaccines will be administered intramuscularly by a study vaccine administrator. The date and time of each study vaccine administration and the location used will be recorded in the eCRF. Subjects will not be allowed to administer the vaccine to themselves or others. Study subjects found

to be significantly non-compliant with study procedures will not be offered to receive the Janssen Ad26.COv2.s vaccine.

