6.1.3 Baseline Visit (-4/+1 Day)

Subjects will return to Mayo Clinic for an in-person visit. Prior to receiving the Janssen Ad26.COVID-19 vaccine, the following study procedures will be performed:

- Serum pregnancy test for females of childbearing potential.
- Platelet count

- Mechanistic Studies
- Tacrolimus, Cyclosporine and MMF serum drug levels in subjects who are receiving these drugs or who were receiving these drugs at the time of enrollment.
- Anti-SARS-CoV-2 spike protein antibody and anti-SARS-CoV-2 nucleocapsid total antibody test
- The participant will have a nephrology consult and a complete physical exam (including review of concomitant medications and immunosuppression). The nephrologist will confirm with the IS reduction group that they have complied with their new medication regimen.
- Vital Signs (heart rate, blood pressure, temperature, pulse oximetry, height and weight).
- Asked if they are experiencing any COVID-19 symptoms or have been recently tested.

Eligible subjects will be vaccinated after these procedures have been completed. The following study procedures can be completed at any time during the visit:

- Study team will record concomitant medications and therapies.
- Study team will document immunosuppression medication
- Patient Status and Graft Status
- Risk Factor Assessment (see Section 14.5)
- Safety Follow Up Questionnaires (questions related to potential GBS, TTS, myocarditis and pericarditis symptoms)
- Kidney Transplant Follow-Up Questionnaire

To differentiate symptoms potentially related to the Janssen Ad26.COV2.S vaccine, the participant will be asked about any symptoms they may currently be experiencing prior to vaccination as well as after to differentiate potential vaccine related adverse events. Then they will receive the Janssen Ad26.COV2.S vaccine during a clinical appointment. All vaccination will be monitored post vaccine for 30 minutes for potential reactions to the vaccination.

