8.1 Confidentiality

Information about study subjects will be kept confidential and managed according to the requirements of the Health Insurance Portability and Accountability Act of 1996 (HIPAA). Those regulations require a signed subject authorization informing the subject of the following:

- What protected health information (PHI) will be collected from subjects in this study
- Who will have access to that information and why
- Who will use or disclose that information
- The rights of a research subject to revoke their authorization for use of their PHI

If a subject revokes authorization to collect or use PHI, the sponsor-investigator, by regulation, retains the ability to use all information collected prior to the revocation of subject authorization. For subjects that have revoked authorization to collect or use PHI, attempts should be made to obtain permission to collect at least vital status (long term survival status that the subject is alive) at the end of their scheduled study period.

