8.5 Data Processing

A data coordinating group will monitor data collection and provide interim analyses to the Data Safety Monitoring Board. **We expect to complete Segment I enrollment within 6-9 months and have final data on the primary endpoint approximately 12 months from study start.** All patient outcome variables are tracked using registries set up in the “Healthy Planet” tool in the Electronic Health Record. For infection data, a registry flags patients as having an infection if a clinical diagnosis of COVID-19 was added to the problem list or a SARS-CoV-2 polymerase chain reaction test is positive. Those without laboratory confirmation are reviewed to ensure that this was appropriate (for example, an outside laboratory result not visible in our chart). External results could satisfy registry metrics if they could be identified within the interoperable framework for data sharing across the EHR, Care Everywhere (Epic Systems Corporation). A similar registry architecture captures data on vaccination data, populated from both EHR records, state health registries, and the health information exchange.

Data Security and Confidentiality

Source documents, CRFs and original consents will be stored in secured locations at Mayo Clinic. Clinical laboratory values are stored in the electronic medical record system requiring protected password access and approved use. Every individual who accesses a medical record has their activity tracked in the system. These data are monitored regularly for access and a formal policy regarding protection of personal privacy which is in place throughout Mayo Clinic.

Data Quality Assurance

Manual and computerized quality checks will occur during data collection and analyses and any discrepancies will require Case Report Form (CRF) review and validation of correct data.

Data Clarification Process

All queries will be logged and tracked electronically, as well as any corrections or justifications which are made, if applicable.

Records Retention

The sponsor-investigator will maintain records and essential documents related to the conduct of the study. These will include subject case histories and regulatory documents.

The sponsor-investigator will retain the specified records and reports for

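### Withdrawal for non-compliance ends data collection after open-label randomization, probably more often in the adjustment arm, and a completer-based primary analysis lets this bias the comparison

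*Combined protocol and SAP*

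**What the plan says.** Section 4.4.1 requires withdrawal from the study for several reasons, among them loss to follow-up and "Repeated failure to comply with protocol requirements". For a withdrawn participant, "no further study data will be acquired but their clinical care will continue as usual". Section 4.4.2 repeats the data stop and asks that the reason be recorded.

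Three other rules bear on who reaches the primary endpoint:
- Section 5.5: subjects found "to be significantly non-compliant with study procedures will not be offered to receive the Janssen" vaccine.
- Section 4.5: a participant who cannot be dosed within the 28-day screening window is discontinued and not rescreened.
- Section 6.9: the primary population is the all-completed one, meaning randomized non-responders who completed what the primary endpoint requires. An all-randomized population is listed, but no analysis is assigned to it. Non-compliance is answered only by saying that the study has enough power.

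Before dosing, the arms are treated differently. Section 6.1.2 gives a Day -14 contact and a regimen change to the adjustment arm alone. At the baseline visit (6.1.3), "The nephrologist will confirm with the IS reduction group that they have complied with their new medication regimen". Under 5.2.2 the no-change arm is simply vaccinated two weeks after randomization.

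On replacement, 4.4.1 says only this: "If a patient is withdrawn, but has already received the Janssen Ad26.CoV2.S vaccine, they will not be replaced by another patient".

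**The concern.** The rules join two decisions that are better kept apart: stopping study procedures, and stopping the collection of outcomes. Once they are joined, a patient's behaviour after open-label randomization can decide whether the outcome exists at all.

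Both arms can break the rules, but the adjustment arm has more to comply with before dosing and is the only arm checked on it. If removal is unequal, and removed patients differ in their chance of response, a completer comparison no longer compares the groups that were randomized. Extra power does not cure this. Nor can the analysis set be changed afterwards to recover it, because the missing data were never collected.

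The loss goes beyond Day 28. Section 3.6 counts hospitalization, patient survival and graft survival to 2 years from randomization, so withdrawn randomized patients belong in those endpoints.

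**Working it through.** **1. The plan's own figures.** Inputs from section 6.7: 150 per arm, two-sided alpha 0.05, arcsine square-root effect size.
- Effect size: h = 2·asin(√p2) − 2·asin(√p1). Power ≈ Φ(h·√(n/2) − 1.96).
- 20% vs 37%: power 0.909 (pooled normal approximation 0.907). Stated: 0.90.
- 20% vs 60%: n = 2(1.960 + 1.282)²/h² = 29.4, rounded up to 30 per arm. Stated: 30.

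The sample size is not in error.

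**2. Completer analysis when there is no true effect.** The documents give no non-compliance rate, so the following are assumptions. Both arms would respond at 20%. A fraction f is removed from the adjustment arm only. Those removed would have responded at rate r. The observed adjustment-arm rate is then (0.20 − f·r)/(1 − f). The rejection rate uses the pooled two-sided chi-square normal approximation with 150 controls and 150(1 − f) adjusted patients.

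| f (patients of 150) | r | Observed rate | Shift (points) | Type I error |
|---|---|---|---|---|
| 10% (15) | 10% | (0.20 − 0.01)/0.90 = 21.1% | +1.1 | 5.6% |
| 10% (15) | 0% | 0.20/0.90 = 22.2% | +2.2 | 7.5% |
| 20% (30) | 10% | (0.20 − 0.02)/0.80 = 22.5% | +2.5 | 8.0% |
| 20% (30) | 0% | 0.20/0.80 = 25.0% | +5.0 | 16.8% |
| 20% (30) | 20% | (0.20 − 0.04)/0.80 = 20.0% | 0 | 5.0% |
| 20% (30) | 40% | (0.20 − 0.08)/0.80 = 15.0% | −5.0 | 18.4% |

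At f = 5% and r = 0 the shift is +1.1 points and type I error is 5.6%. Refilling the arm to 150 does not help: at f = 20% and r = 0 the error is 17.9%. If both arms lost the same fraction of the same kind of patient, both observed rates would follow the same formula and the shifts would cancel. The harm therefore depends on unequal removal.

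**3. Cost of analysing all randomized patients.** Undosed adjustment-arm patients count as non-responders, and all controls are dosed. The adjustment-arm rate becomes (1 − f) × 37% or (1 − f) × 60%.

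| f | 20% vs 37%: rate, power | 20% vs 60%: rate, power |
|---|---|---|
| 5% | 35.2%, 0.84 | 57%, above 0.999 |
| 10% | 33.3%, 0.75 | 54%, above 0.999 |
| 15% | 31.5%, 0.63 | 51%, above 0.999 |
| 30% | 25.9%, 0.23 | 42%, 0.987 |

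These are the cost of the remedy, not damage done by the present rule.

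**The case against.** The rules are neutral on their face. Travel, diaries, calls and Day 14 and 28 samples bind both arms. Section 4.4.1 needs repeated failure, whereas 6.1.3 describes a single confirmation, and nothing says that failing it bars dosing or triggers withdrawal. Section 4.2 excludes patients judged unlikely to adhere, and 6.9 does not expect much non-compliance. Controls without a Day 28 result also drop out of the completer set. All of this stands. It limits the claim to likely unequal exposure.

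Several stronger readings are tempting but not supported:
- *The rule filters one arm.* That is an inference from the pre-dose schedule, not something the text states.
- *Patients removed before dosing are replaced.* Section 3.2 counts the target in vaccinated subjects, which hints at it, but 4.3 closes screening once 400 have enrolled in Segment I and 3.1.1 fixes 150 per arm. Replacement is neither stated nor excluded.
- *Removed patients leave no trace.* Section 4.4.2 requires the reason in the eCRF and source document, and 6.9 lists the randomized population separately.
- *Section 3.3 is contradicted.* Its sentence "Screened patients not receiving the Janssen Ad26.CoV2.S vaccine will be followed for 2 years" most naturally means the initial responders, as 3.1.3 and 3.2 show.
- *Section 8.1 is contradicted.* There, "attempts should be made to obtain permission to collect at least vital status" concerns revoked authorization and a fresh request for permission. It can coexist with 4.4.1.
- *Removed patients would still respond at 20%.* In 6.7 that is a rate after vaccination, so it does not fit patients from whom the vaccine is withheld.

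One could add that the record system would capture late outcomes anyway, since by 8.5 "All patient outcome variables are tracked using registries set up in the" electronic health record. But 4.4.1 stops acquisition of study data, so as written those outcomes could not be used.

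**Conclusion.** The point holds in limited form. As written, the plan discards Day 28 and 2-year outcomes of some randomized patients for reasons that arise after open-label allocation, in a way that can differ by arm, and its primary analysis is restricted to completers.

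Size and direction cannot be known from the documents. The shift of about +1 to +5 points and the type I error of about 5.6-17% rest on three assumptions: 10-20% removal, removal in the adjustment arm only, and would-be response of 0-10% in those removed. With response equal to the rest there is no bias; with better response it reverses.

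This is a worthwhile, inexpensive correction rather than a fatal flaw. The plan already takes the better course elsewhere: 5.6 keeps patients given prohibited therapy in the study, and 7.5 keeps patients whose vaccination is stopped under follow-up.

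**What to change.** - **4.4.1 and 4.4.2:** let only withdrawal of consent end data collection. Non-compliant patients, and those lost to contact where possible, keep the Day 28 spike sample if dosed, using the mailed kits already described in section 6, and record or registry follow-up to 2 years (6.1.7, 8.5).
- **Replacement:** state that no randomized patient is replaced, dosed or not.
- **6.9:** make all randomized patients, analysed as assigned, the primary population. Count undosed patients as non-responders, because the endpoint is timed from vaccination and has no date for them. State in advance how a dosed patient without a Day 28 result is counted. Keep completers as a sensitivity analysis.
- **Compliance:** record compliance with the adjustment.
- **Consistency:** reconcile 4.4.1, 4.4.2, 4.5, 5.5, 6.9 and 7.5. Whether a non-compliant patient is dosed is for the sponsor to settle.

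The cost is some rewording, a few more kits and chart reviews, and a somewhat smaller reported effect. Power at 20% vs 37% would fall to about 0.84, 0.75 and 0.63 with 5%, 10% and 15% undosed in the adjustment arm. At the plan's expected 20% vs 60% it stays at about 98.7% or more even with 30% undosed.
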